Accrual Objective: We will enroll 138 cancer patients, with half in the intervention arm and half in the control arm. Our primary endpoint is the PROMIS 4-item Fatigue Short Form. The age- and sex-adjusted norm for the Fatigue scale is 50 points, with a standard deviation of 10 points. These statistics have been shown to be largely generalizable to the cancer patient population (mean: 52, standard deviation 7.6). Our study will have power of 0.80, assuming a two-sided Type I error rate of 0.05, to detect an effect size of half the standard deviation between the intervention and control arms if 64 cancer patients are enrolled in each of the control and intervention groups. A mean difference of one-half a standard deviation is clinically meaningful and is considered a medium effect size for clinical trials. During the primary analysis, we will adjust for the fact that there are three cancer populations in our data and will look for a well-defined effect that is marginal within each population. We will accrue a total of 69 patients in each arm to account for attrition of data, assuming a 7% dropout rate from the trial.

Accrual Period: The estimated accrual period is 1.5 years

Study Duration: Data will be collected from participants for 12 weeks. Passive collection of wearable data through the app will continue for up to one year for each participant who opts-in to continue using the app, and medical records may be accessed for up to five years after the conclusion of the 12-week collection period.

STUDY SCHEMA: SCHEDULE OF EVENTS

[figure not shown]

Diagram outlining the survey data collected over the trial. Note: "Control actions" here refers to following "dummy" lighting recommendations that are minimally expected to affect the circadian clock.

TIME AND EVENTS TABLE

Patient Events Timeline			
Every day after starting the trial:	Every week, starting on the first day of the trial:	On the first day and last day of the trial:	At any point in time:
Single question daily fatigue survey	PROMIS Fatigue survey, "How is your experience with the app?" questionnaire, sleep aid usage survey	PROMIS Sleep, Anxiety, Depression, Physical Function, Global Health	App experience free response

Study Timeline	Year 1				Year 2			
	Q1	Q2	Q3	Q4	Q1	Q2	Q3	Q4
Revise the app to include the capacity to collect survey responses	X	X						
Begin identifying potential subjects using UofM Health Research website		X						

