1. STUDY DESIGN

- 1.1. *Study Overview.* This study will use a two-arm randomized study design. Participants will be recruited across three cancer types. Each of the participants will be randomized to an active “intervention” arm (using the full SYNC app) or to a control arm (using a “dummy” version of the SYNC app that gives recommendations for light at times that should not significantly affect the circadian clock). The random allocation of participants to the treatment arm or control arm establishes the basis for testing the statistical significance or difference between the groups in the measured outcome (patient fatigue, assessed by a daily 1-question fatigue survey and the PROMIS 4-item Fatigue). Patient age, gender, and other prognostic baseline characteristics that could potentially confound an observed association, including those that are unknown or unmeasured, will be distributed equally, except through chance alone, through random assignment. Thus, this design is well-suited to our goal of assessing the efficacy of a mobile health intervention, SYNC, on participants.
- 1.2. *Primary Hypothesis.* The primary hypothesis is that a mobile-app delivered circadian intervention (SYNC) will reduce patient fatigue.
- 1.3. *Study Objectives*
 - 1.3.1. Primary Objective. To test the difference between the “intervention” (full SYNC app) arm and the control (limited SYNC app) arm in the measured outcome of patient fatigue, assessed by daily 1 question surveys and weekly 4-item PROMIS questionnaires over the course of 12 weeks.
 - 1.3.2. Secondary Objective. To determine the change in sleep disturbances, anxiety, depression, physical functioning, and global health through PROMIS questionnaires, between baseline and the 12-week assessment in both the control and intervention arms, and to look for differences in this change between the two arms.
 - 1.3.3. Exploratory Objectives
 - 1.3.3.1. Change in patient physical activity through physiological data capture using the wearable sensors in the control versus intervention arm.
 - 1.3.3.2. Change in patient health care utilization (e.g., total count of hospital days, readmissions, and ambulatory care clinic visits) in the control versus intervention arm
 - 1.3.3.3. Change in patient sleep aid usage in the control versus intervention arm.
- 1.4. *Participant Eligibility*
 - 1.4.1. Inclusion Criteria

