4. PATIENT ENROLLMENT AND EVALUATION

- 4.1. Study participants will be recruited through the following means:
 - (1) The University of Michigan Rogel Cancer Center physicians, advanced practice providers, and nurse coordinators.
 - (2) The University of Michigan health system's electronic health record (EHR) is based on the Epic software (MiChart), which allows researchers, with IRB approval, to contact (via email, flyers, phone calls, or in-person) individuals who meet specific criteria and may be eligible to participate in the study. For example, with IRB-approval, Drs. [name], [name], and [name] and their Research Staff can access the daily clinic schedules, which will enable them to identify potential participants and meet them in-person during a corresponding patient encounter.
 - (3) With IRB-approval, we will distribute flyers in the outpatient clinics for our three cancer populations to inform potential individuals about the study. We will also distribute emails to potential study participants via the University of Michigan's UMHealthResearch (<https://umhealthresearch.org>) service.
 - (4) The Michigan Institute for Clinical and Health Research (MICHR), supported by the NIH Clinical and Translational Science Award Program, will assist our team with developing and reviewing recruitment materials, and identifying obstacles that may affect participant recruitment and retention.
- 4.2. *Randomization*: Once the patient is deemed eligible and has provided written informed consent, the Research Coordinator will confirm eligibility. The study statistician, [name], will create a randomization list before the study begins enrollment using the statistical package R. [name] will then forward the list to the Data Manager, who will be responsible for enrolling patients and assigning them to the correct study arm.
- 4.3. *Pre-Intervention Evaluation*: PROMIS Patient-Reported Outcomes (PROs) – Well-being or HRQOL assessments will be obtained at baseline, pre-intervention. The surveys will be completed directly through the SYNC app on mobile phones. Based on prior work, our Study Team has experience administering PROMIS PROs on mobile devices.

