5.12. *Analysis of Primary Endpoint.* Analysis will be an intent-to-treat analysis that includes all participants. Mean Global Health scores at the end of the trial will be compared using a two-sample *t*-test (or Wilcoxon Rank Sum test if non-normality is apparent) with a significance level of 0.05. Linear regression models will be performed to complement the results of the *t*-test and adjust for specific baseline participant's characteristics (e.g., demographic, social, environmental) to increase the precision of our inference. There is a possibility that patient characteristics will be unbalanced since our randomization scheme will be applied to participants. Thus, our models also will assess potential moderating or mediating effects.

5.13. *Analysis of Secondary Endpoint.*

Mean PROMIS scores (PROMIS sleep disturbances, anxiety, depression, physical function, and global health) for each arm at the end of the trial will be compared using a two-sample *t*-test (or Wilcoxon Rank Sum test if non-normality is apparent) with a significance level of 0.05. Linear regression models will be performed to complement the results of the *t*-test and adjust for specific baseline participant's characteristics (e.g., demographic, social, environmental) to increase the precision of our inference. There is a possibility that patient characteristics will be unbalanced since our randomization scheme will be applied to participants. Thus, our models also will assess potential moderating or mediating effects.

5.14. *Analysis of Exploratory Endpoints.*

5.14.1. Patient activity. The accelerometer data of each subject will be transformed into a low-dimensional representation using motif discovery algorithms.⁷⁹ Such techniques are completely data-driven, and search for motifs (i.e., patterns) in the data that occur more often than chance. A signal can then be represented by the number of times a particular motif occurs. Others have successfully used such techniques for representing a variety of waveform data, including accelerometer and continuous glucose data.⁸⁰⁻⁸² The accelerometer data will be processed to derive estimates of total sleep duration (i.e., hours per night), wake after sleep onset, and sleep efficiency (i.e., ratio of sleep to wake). The variables will be compared between arms.

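### Secondary objective 1.3.2 asks about change from baseline, but 5.13 tests end-of-trial means, names no day-1 score as covariate and plans no within-arm change

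*Combined protocol and SAP*

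**What the plan says.** - **Objective (Study Design 1.3.2).** For sleep disturbance, anxiety, depression, physical function and global health, the plan is to determine change "between baseline and the 12-week assessment in both the control and intervention arms", "and to look for differences in this change between the two arms".
- **Data collection.** The Time and Events Table schedules "PROMIS Sleep, Anxiety, Depression, Physical Function, Global Health" under the column "On the first day and last day of the trial". Section 4.3 states that the PROMIS "assessments will be obtained at baseline, pre-intervention", and 4.4 repeats the assessment at 12 weeks.
- **Analysis (5.13).** Mean scores on the five scales "for each arm at the end of the trial will be compared using a two-sample" t-test, or by a Wilcoxon rank sum test if the data look non-normal, at the 0.05 level. Linear regressions complement this test and will "adjust for specific baseline participant's characteristics (e.g., demographic, social, environmental) to increase the precision of our inference".
- **Elsewhere.** Section 5.11.1 makes completion of the baseline measures a condition for the analysis population. Section 5.1 fills missing values with the participant's last available value.
- **Sample size (5.7).** The calculation is for PROMIS Fatigue. No power, effect size or correlation is given for the secondary scales.

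**The concern.** The objective and its test do not match. Section 5.13 defines no change score and no within-arm change, and the only covariates it names are demographic, social and environmental examples. The day-1 score on the same scale is usually the strongest predictor of the week-12 score, and it is already collected.

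Three things are at stake:

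- The within-arm part of 1.3.2 has no planned result.
- The between-arm part is answered with less precision than the data allow, and a chance day-1 difference passes partly into the end-of-trial comparison.
- For five scales it stays open whether the end score, the change or an adjusted score will be emphasised.

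**Working it through.** **1. The plan's own figure (5.7, fatigue).** Inputs: half-SD difference, two-sided 0.05, power 0.80, 1:1 allocation. The exact two-sample t calculation gives 63.77, so 64 per arm, with power 0.801 at 64. With 7% dropout, 64 / 0.93 = 68.8, so 69 per arm. Both stated figures reproduce.

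**2. Do the two contrasts estimate the same effect?** In a simulation of 20,000 randomized trials (64 per arm, day-1 to week-12 correlation r = 0.5, true effect −0.5 SD), the end-of-trial difference averaged −0.499 (SE 0.177) and the difference in change −0.499 (SE 0.177). Under randomization they do.

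**3. Precision.** Assumptions: equal SDs at both times, 64 per arm, half-SD difference, two-sided 0.05, and r assumed. Relative to an end-of-trial mean, the variance is multiplied by 2(1 − r) for a change score and by 1 − r² for the week-12 score adjusted for its day-1 value (ANCOVA). The standardized difference is 0.5 divided by the square root of that factor.

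| r | Power, end means | Change: variance factor | Power, change | ANCOVA: variance factor | Power, ANCOVA |
|---|---|---|---|---|---|
| 0.3 | 0.80 | 1.40 | 0.66 | 0.91 | 0.84 |
| 0.5 | 0.80 | 1.00 | 0.80 | 0.75 | 0.90 |
| 0.7 | 0.80 | 0.60 | 0.95 | 0.51 | 0.98 |

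Since 1 − r² never exceeds 1, and 2(1 − r) − (1 − r²) = (1 − r)² is never negative, ANCOVA is at least as precise as either alternative at every r, apart from one degree of freedom.

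**4. ANCOVA answers the change question.** Write the model as Y12 = a + b·arm + g·Y0. Subtracting Y0 from both sides gives Y12 − Y0 = a + b·arm + (g − 1)·Y0. The arm coefficient b is the same, so it is also the baseline-adjusted difference in change.

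**5. Chance day-1 imbalance.** The SE of the day-1 gap is SD × √(2/64). The 2.5-point threshold is chosen for illustration. Both SDs come from 5.7: 10 is the general norm, and 7.6 is the cancer-population value for fatigue.

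- SD 10: SE = 1.77, z = 2.5 / 1.77 = 1.41, chance 0.157 per scale. At least one of five: 1 − (1 − 0.157)^5 = 0.575.
- SD 7.6: SE = 1.34, z = 2.5 / 1.34 = 1.86, chance 0.063 per scale. At least one of five: 1 − (1 − 0.063)^5 = 0.28.

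The five-scale figures assume independence, and positive correlation between scales lowers them. If such a gap occurs, the part carried into the end-of-trial difference is r × gap, for example 0.6 × 2.5 = 1.5 points at r = 0.6.

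**The case against.** The strongest defence is that randomization makes the end-of-trial difference and the difference in change estimate the same effect, so the between-arm question is answered, and by a valid test. That stands. The t-test's standard error already allows for chance imbalance, so the carry-over in step 5 is conditional on a gap having occurred and is not a bias of the procedure.

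Several further points stand as limits:

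- Section 5.13 does plan regressions, and its covariate list is only of examples. The day-1 score is left unspecified, not excluded.
- The change wording appears only in 1.3.2. The synopsis speaks of assessing these domains, and 3.2 lists the instruments without defining change.
- Section 5.1 promises descriptive statistics, where a within-arm summary could be placed, although change is not mentioned there.
- A raw change-score test, the most literal reading of 1.3.2, would have less power than end means when r is below 0.5 (0.66 against 0.80 at r = 0.3). The gains above belong to ANCOVA and do not measure the cost of the mismatch itself.
- The 64 per arm and the half-SD difference are borrowed from the fatigue calculation.

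A reader might infer that the secondary question is not analysed at all, or that the day-1 scores go unused. The documents support neither. The between-arm effect is estimated. The day-1 scores help define the analysis population (5.11.1) and, for forms given only twice, are the values that 5.1 carries forward. None of these points supplies a planned within-arm change or commits 5.13 to the day-1 covariate.

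**Conclusion.** The point holds as a mismatch between objective 1.3.2 and section 5.13, with a free improvement available. No within-arm change analysis is specified. The between-arm test is valid and unbiased, but less precise than a baseline-adjusted one whenever the day-1 and week-12 scores are correlated.

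The size is illustrative. Power rises from 0.80 to between 0.84 and 0.98 for assumed r of 0.3 to 0.7, given 64 per arm, a half-SD difference and equal SDs. The chance of a day-1 gap above 2.5 points on at least one scale is about 28% to 58%, depending on the SD and assuming independent scales. A reader might infer that a visible imbalance is likely. That follows only at SD 10 with independent scales, and the documents give no SD from cancer patients for any of the five.

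**What to change.** In 5.13:

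1. Make the main between-arm analysis of each scale a linear model of the week-12 T-score on arm and that scale's day-1 T-score. Report the arm coefficient with its 95% CI as the baseline-adjusted difference in change.
2. Report mean change with 95% CI within each arm, labelled descriptive. Under 5.1, a participant without week-12 forms would be given a change of zero, so state how many values are carried forward.
3. Keep the unadjusted end-of-trial test as supportive.

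The cost is a few lines of SAP wording and one covariate per model, settled before the data are locked. No new forms, visits or participants are needed, because the day-1 forms are scheduled and 5.11.1 already requires the baseline measures.

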Eligibility Criteria: All patients will be outpatient, though most will still be undergoing long-term treatment: breast cancer patients often receive endocrine therapy; prostate cancer patients often receive androgen deprivation therapy; and HSCT patients will be recovering their immune system from the high-dose chemotherapy that was administered in preparation for their transplant. We will exclude patients actively receiving chemotherapy at the time of enrollment to avoid potential confounding factors. However, post-transplant maintenance chemotherapy will be allowed. We will also exclude night shift workers, where night shift work is defined as working a significant number of hours (i.e. more than half) between the hours of 11PM and 6AM on a regular basis. Participants will be required to be able to read and write English, be at least 18 years old, and report their baseline fatigue level as

moderate (4 or higher on a 10-point scale). Patients must own an iPhone 6s or later (with iOS 14 or later, or willing to update to iOS 14+) and be able to complete surveys on it, or they must agree to utilize a loaner iPhone provided by the study team to use during the study and return at the end of the study.

Treatment Description: All participants will be given access to an app into which they enter their research ID number. The research ID number will determine which version of the app is loaded on their phone. Participants will also be given a wearable device and a pair of glasses. Interventional group participants will be given a pair of blue light-blocking glasses. Participants in the control group will be given a pair of glasses that does not block visible light. All participants will wear the wearable device day and night over the course of the 12-week trial. Participants in the interventional group will use a version of the app that gives them personalized lighting recommendations (e.g. "Seek bright light") and a time interval over which the recommendation applies (e.g. "8:30 - 9:45 am").

Control arm: Control group participants will use a version of the app that makes recommendations to use the glasses; however, the time intervals recommended will be chosen to occur in the period of time when any change in lighting is expected to have no effect on the circadian clock (e.g. around noon, for many people already entrained to a diurnal schedule). Participants will be informed that they should only wear the glasses if it is reasonable for them to do so.

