3. STUDY ENDPOINTS

3.1. *Primary Endpoint.* The primary endpoint is **fatigue**, as assessed by a daily fatigue questionnaire and a weekly 4-item PROMIS fatigue questionnaire.

3.2. *Secondary Endpoint.* The secondary endpoints are sleep disturbance, anxiety, depression, physical function and global health, as measured via the following PROMIS validated instruments:

- PROMIS Sleep Disturbance (8-item)
- PROMIS Anxiety (7-item)
- PROMIS Depression (8-item)
- PROMIS Physical Function (8-item)
- PROMIS Global Health (10-item)

3.3. *Exploratory Endpoints.*

3.3.1. Activity data. Patient activity (steps) and sleep will be measured continuously from the start to the end of the trial through wearable sensors.

3.3.2. Health care utilization data. Patient health care utilization data (e.g., total count of hospital days, emergency department visits, readmissions, and ambulatory care clinic visits) will be captured through the electronic health record as well as self-report (i.e., if the patient is readmitted at an outside hospital other than Michigan Medicine).

3.3.3. Sleep aid utilization data will be collected via self-report in the app once a week.

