- 5.6. *Primary Endpoint.* The primary objective of the study is to test the effects of SYNC in a randomized controlled clinical trial design. Patients will be randomly assigned to the treatment arm or the control arm. The primary objective is to quantify the effects of the light interventions delivered by SYNC on patient fatigue.
- 5.7. *Sample Size Considerations.* We will enroll 138 cancer patients, with half in the intervention arm and half in the control arm. Our primary endpoint is the PROMIS 4-item Fatigue Short Form. The age- and sex-adjusted norm for the Fatigue scale is 50 points, with a standard deviation of 10 points. These statistics have been shown to be largely generalizable to the cancer patient population (mean: 52, standard deviation 7.6). Our study will have power of 0.80, assuming a two-sided Type I error rate of 0.05, to detect an effect size of half the standard deviation between the intervention and control arms if 64 cancer patients are enrolled in each of the control and intervention groups. A mean difference of one-half a standard deviation is clinically meaningful and is considered a medium effect size for clinical trials. During the primary analysis, we will adjust for the fact

that there are three cancer populations in our data and will look for a well-defined effect that is marginal within each population. We will accrue a total of 69 patients in each arm to account for attrition of data, assuming a 7% dropout rate from the trial.

5.8. PROMIS® measures use Item Response Theory (IRT), a family of statistical models that link individual questions to a presumed underlying trait or concept of global health represented by all items in the scale. PROMIS® instruments are scored using item-level calibrations. The most accurate way to score a PROMIS® instrument is to use the Health Measures Scoring Service, which our Study Team has experience with. This method of scoring uses “response pattern scoring,” which uses responses to each item for each participant. Response pattern scoring is especially useful when there is missing data (i.e., a respondent skipped an item), or different groups of participants responded to different items).

There are four key features of the score for PROMIS® Fatigue:

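### Section 5.14.1 defines the exploratory variable sleep efficiency as sleep divided by wake, which is the odds of being asleep and not the share of the sleep period spent asleep

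*Combined protocol and SAP*

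**What the plan says.** Section 5.14.1 (Patient activity) lists three sleep variables to be obtained from the accelerometer. The last of them is given as "sleep efficiency (i.e., ratio of sleep to wake" (the source closes the bracket there). The abbreviation i.e. makes this a definition and not an example, and no other place in the document defines sleep efficiency. The other two variables, a nightly duration and the wake that follows sleep onset, carry no such formula.

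The analysis is a single sentence: "The variables will be compared between arms". It names no test, transformation, summary over nights, or rule for a night without recorded wake.

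Section 3.3.1 places wearable sleep among the exploratory endpoints: "Patient activity (steps) and sleep will be measured continuously from the start to the end of the trial through wearable sensors". The sleep outcome at secondary level is a different one, the PROMIS Sleep Disturbance form in section 3.2.

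**The concern.** Sleep efficiency is a share: time asleep over the length of the sleep period, between 0 and 1. Sleep over wake has no upper limit, rises steeply as wake becomes small, and cannot be computed at zero wake. An analyst who follows section 5.14.1 literally would report, under the name sleep efficiency, a figure on a different scale whose mean depends mostly on the patients or nights with least recorded wake. At stake is whether one exploratory result can be read, in a trial whose intervention acts on the circadian clock and whose full app gives advice on sleep times.

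**Working it through.** The plan states no numerical value for sleep efficiency, so there is no figure to reproduce. The check is algebra, worked nights and a simulation.

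**Inputs from the document.** The definition and companion variables in section 5.14.1; 69 patients per arm (section 5.7: "We will accrue a total of 69 patients in each arm to account for attrition of data, assuming a 7% dropout rate from the trial").

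**Assumed inputs, not in the document.** Efficiency follows a beta distribution with mean 0.85; the SD is varied from 0.03 to 0.10. In the simulated trials wake is floored at 1/480 of the sleep period.

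**1. Algebra.** Let S be sleep and W be wake within the nightly sleep period. Efficiency is E = S/(S+W). The quantity as written is S/W = E/(1−E), which runs from 0 to infinity.

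**2. Single nights with S = 420 min.**

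| Wake (min) | S/(S+W) | S/W |
|---|---|---|
| 60 | 420/480 = 0.875 | 7 |
| 30 | 420/450 = 0.933 | 14 |
| 5 | 420/425 = 0.988 | 84 |
| 1 | 420/421 = 0.998 | 420 |
| 0 | 1 | undefined |

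Between 5 and 1 min of wake the share moves by 0.009 (0.9976 − 0.9882) and the ratio moves from 84 to 420.

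**3. Averages over nights can reverse the order of two patients.**

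- Patient A, nights of 456/24 and 360/120 min (sleep/wake): efficiency (0.95 + 0.75)/2 = 0.85; ratio (19 + 3)/2 = 11.0.
- Patient B, two nights of 432/48 min: efficiency 0.90; ratio 9.0.

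A sleeps less efficiently but has the higher mean ratio. If A's nights are first added up, the ratio is 816/144 = 5.7, below B's 9.0, and the order is right again. The reversal comes from averaging nightly ratios.

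**4. Skewness of the ratio, mean efficiency 0.85.** For SD 0.03, 0.04, 0.05 and 0.06 the population skewness is about 1.0, 1.5, 2.1 and a little over 3. In samples of 69 the average skewness is lower, about 2.0 at SD 0.06.

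**5. Simulated trials, 69 per arm, one value per patient, 2,000 runs per setting.**

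| SD of efficiency | Share of within-arm sum of squares carried by the 3 largest ratios | Sign of mean difference differs between S/W and S/(S+W), arms truly equal |
|---|---|---|
| 0.05 | 41% | 15% |
| 0.07 | 54% | 23% |
| 0.10 | 72% | 35% |

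With a true shift of half an SD, the signs differed in only 0.1% to 0.2% of trials.

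**6. Operating characteristics in the same simulation.** Type I error of the t-test on S/W was 0.033 to 0.054. For a true half-SD shift its power was 0.88 to 0.96, against 0.83 on S/(S+W). The rank-sum test rejected at the same rate on both forms, as it must, because one is an increasing function of the other.

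**The case against.** The strongest reply is that this is a loose gloss on an exploratory variable, with limited consequences. Much of that stands.

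- With one value per patient taken from total sleep and total wake, the ratio is a one-to-one transform of efficiency, so a rank test gives the same answer. Section 5.14.1 does not commit to means. Sections 5.12 and 5.13 allow a Wilcoxon test under non-normality; this is not extended to 5.14.1, but it shows that the plan contemplates more than means.
- No harm to the test was found: type I error was not inflated and power was not reduced.
- Total sleep duration and wake after sleep onset are derived separately, and the PROMIS sleep outcome is untouched.
- The skewness and simulation results rest on an assumed distribution. The simulation has no nights within patients, so it speaks to extreme patients; only the worked example in step 3 speaks to extreme nights.

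A reader might also infer that wake covers the whole 24 hours, because the synopsis says "All participants will wear the wearable device day and night over the course of the 12-week trial". Seven hours of sleep would then give 7/17 = 0.41, merely a restatement of sleep duration. The text does not support this reading. The two variables listed just before are a duration per night and wake after sleep onset, both nightly quantities, and the synopsis sentence concerns wearing the device, not the meaning of wake.

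The reply does not rescue the definition. It is explicit, nothing corrects it, and a number produced by it cannot be read as sleep efficiency.

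**Conclusion.** The definition is wrong as written; severity is minor. The algebra and the worked nights need no assumption beyond reading wake as wake within the sleep period: the stated quantity is an odds, is undefined at zero wake, and can misorder patients when nightly values are averaged. How far extreme values drive the arm means depends on the spread of efficiency in these patients, which the document does not give. At an assumed mean of 0.85 the skewness is about 1.0 to 3 for SD 0.03 to 0.06, and a larger SD makes it worse.

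A reader might go further and infer that the comparison could not measure sleep efficiency at all, or that the test would be invalid or underpowered. Neither follows. The first holds for means and for averages of nightly ratios, not for a rank test on one value per patient; the second is contradicted by the simulation. The fatigue analysis, its sample size and the secondary PROMIS comparisons do not depend on this variable.

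**What to change.** In section 5.14.1, replace the sleep-to-wake ratio by total sleep time divided by the sum of total sleep time and wake within the nightly sleep period. State that this period is derived from the device and is the same window used for wake after sleep onset. That matters because no survey in Appendix C collects nightly bed and rise times, so a definition that needs self-reported bedtimes could not be applied. State also that nights are summarised to one value per patient before the arms are compared.

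The cost is a short edit of two or three sentences. It needs no new data collection, since the plan already derives sleep duration and wake after sleep onset, and it leaves the sample size alone. It should be made before the data are locked.
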